The study managers, data manager, PI's, fetal medicine experts and delegated site staff will have access to the anonymised data on the database through the use of usernames and encrypted passwords. In addition to this, access to hard copies of the CRF and questionnaire data will be required by the fetal medicine experts, qualitative researchers and clinical radiologists for study monitoring and audit purposes.

The secure data management system will incorporate quality control procedures to validate the study data. Error reports will be generated where data clarification is required.

13. Publication

Authorship of research papers arising from this study will include co-applicants relevant to the topic, other specific contributors, and a generic reference to all study collaborators; in practice this would read as a list of named authors followed by "...and on behalf of the MERIDIAN study group". All members of the MERIDIAN study group would be named within the appropriate acknowledgements section of the journal article.

Results of the trial will be disseminated in peer reviewed scientific journals and clinical and academic conferences. No report, either verbal or written may be made without the approval of both the TMG and TSC.

Details of the trial will also be made available via a study website. Summaries of the research will be updated periodically to inform readers of the ongoing progress.

14. Finance

The trial has been financed by the Health Technology Assessment (HTA) programme of the National Institute for Health Research (NIHR) and details have been drawn up in a separate agreement.

15. Ethics approval

The trial will be submitted to a Local Research Ethics Committee (LREC) through the IRAS central allocation system. The approval letter from the ethics committee and copy of approved patient information leaflet, consent forms, CRF's and questionnaires will be sent to the Clinical Trials Research Unit (CTRU) in Sheffield before initiation of the study and patient recruitment.

16. Indemnity / Compensation / Insurance

Sheffield Teaching Hospitals NHS Foundation Trust is the sponsor of this research study. The Universities of Sheffield and Newcastle also have in place insurance against liabilities for which they may be legally liable and this cover includes any such liabilities arising out of this research study.

17. References

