Whilst cost effectiveness analysis using the quality adjusted life year (QALY) as the denominator is widely accepted as being of most use to NHS decision makers, and has long been considered standard for bodies such as NICE, the relevance of the QALY to in utero MRI is questionable.

The potential benefits of in utero MRI are varied and include quality of life benefits that may not be well reflected in standard health related quality of life instruments (HRQoL). It is highly likely that the rate of terminations of healthy fetuses will be lower if MRI achieves a lower rate of false positive diagnosis than ultrasound (US). It is also possible that terminations of abnormal fetuses will be higher if MRI achieves a lower rate of false negative diagnosis than ultrasound. We know that decision makers may be uncomfortable with the use of QALYs to reflect the value of an unborn child. This situation raises the additional complication of differential valuation of the unborn child according to the presence or absence of brain abnormalities. There is also the potential for such an approach to lead to the perverse situation of recommending the approach with the lowest rate of true negative detections.

Study Design

A cost consequences analysis will be performed, whereby multiple outcomes are to be presented alongside costs, reflecting the incremental impact of the use of MRI. The study's basecase will take a NHS perspective using a time horizon limited to the due date of the baby. Both societal perspectives and a life-time horizon will be examined in a sensitivity analysis.

Outcome Measures

Incremental cost per management decision appropriately revised after in utero MRI as compared to ultrasound alone

This will be recorded as outlined above from the 2 point categorical management decision. The decision is classified as appropriate if the revised decision is consistent with the presence or otherwise of neuro-developmental abnormalities at birth or post-mortem. So, for example, a change to termination, from no termination, would be considered appropriate if a post mortem were to show neurological abnormalities.

Wider Management Effects

Other secondary outcomes will also be presented alongside the incremental cost-effectiveness ratio, in order that wider effects are considered within the economic analysis. These are:

- 1) Diagnoses correctly revised derived from the US and MRI reporting forms and the results of post-mortem or birth records.

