Unit costs for the three types of consultations will be taken from NHS Reference Costs (<http://www.dh.gov.uk/en/Publicationsandstatistics/Publications/index.htm>). The definitions of the Reference Costs change over time, and so their relevance to our study will be assessed in the final year of the study, with amendments made if necessary through discussion with the Finance Department of Sheffield Teaching Hospitals Trust. Travel costs will be based on cost per mile based for car travel (http://www.theaa.com/motoring_advice/running_costs/index.html), with distance travelled based on the distance between the patient's postcode and the hospital attended. Patient time costs will be based on national average salaries (<http://www.statistics.gov.uk/cci/nscl.asp?id=8242>). Costs associated with long-term costs of care for infants born with brain abnormalities will be gathered from the literature. [Note that the references do not show the precise source, as the most up-to-date figures will be used, which as such, have not yet been produced.]

Analysis

The study will compare the addition of MRI to single US using the incremental cost per management decision appropriately revised, together with additional secondary outcome measures. The ICER will be plotted on the cost-effectiveness plane together with its associated cost-effectiveness acceptability curve. The basecase will only consider the costs and benefits identified directly within the study (i.e. up until the due date of the baby). However, we will also develop a simple decision model that will enable us to consider the potential costs and outcomes of repeat ultrasound (see below) and to incorporate the longer term cost implications of improved diagnosis. In particular, we will review existing literature to provide estimates of the NHS and broader societal cost implications of providing support for children born with the types of brain abnormalities identified as relevant in the study.

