Table 2 below lists the adverse events and serious adverse events which have the potential to occur during this study. These events will be recorded and reported to the DMEC, and as appropriate to the TSC, and they are defined as “expected” events within this study protocol. Nevertheless, the TSC will ultimately judge whether the rate of occurrence of these events is within acceptable and anticipated levels. Any other medical event which occurs during the study which meet the criteria defined above for a SAE will be recorded and reported to the DMEC.

Table 2. Expected SAE’s & AE’s.

Serious adverse event (SAE)	Adverse event (AE)
1) MR diagnosis differs from outcome reference diagnosis; TOP performed	1) MR diagnosis differs from outcome reference diagnosis; US diagnosis same as outcome reference diagnosis
2) Spontaneous intrauterine fetal demise (IUFD) or Stillbirth	2) MR examination incomplete or sub-optimal as a result of patient anxiety and/or claustrophobia
3) Pre-term delivery (less than 37 weeks)	
4) Neonatal death	
5) Injury during MR examination related to pacemaker, medical implant or other metallic object (failure of MR safety screening procedures)	

Perhaps the most important clinical risk associated with this study is that the prospective management of a particular pregnancy is modified as a result of information made available by in utero MR imaging, and this information subsequently proves to be inaccurate. For instance, an abnormality is detected on ultrasound, but the fetal prognosis is not considered so poor as to justify termination of pregnancy; the prognosis based on in utero MR imaging is considered to be much worse, however, to an extent where termination of pregnancy is discussed and subsequently performed (and the following post mortem examination does not substantiate the MR findings). Any such case would only be identified after the reference diagnosis is achieved (for instance by autopsy), and only then during retrospective comparison of prenatal and outcome diagnosis. As soon as any such case is identified,

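### The economic ratio counts only management decisions that MR revised appropriately and does not deduct those it revised wrongly, so its effect measure cannot show net harm

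*Protocol*

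**What the plan says.** Protocol section 4, Health Economics Study, names the main outcome as "Incremental cost per management decision appropriately revised after in utero MRI as compared to ultrasound alone". The decision comes from a binary scale: "This will be recorded as outlined above from the 2 point categorical management decision". The counting rule begins: "The decision is classified as appropriate if the revised decision is consistent with the presence or otherwise of" neurodevelopmental abnormality at birth or post-mortem. The only worked example runs in the favourable direction: "a change to termination, from no termination, would be considered appropriate if a post mortem were to show neurological abnormalities".

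Section 8, under the economic Analysis heading, repeats the unit: "The study will compare the addition of MRI to single US using the incremental cost per management decision appropriately revised". It then says: "The ICER will be plotted on the cost-effectiveness plane together with its associated cost-effectiveness acceptability curve".

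Neither section mentions a decision that matched the outcome on ultrasound and failed to match it after MR. Section 4 does set the ratio in a wider frame: "A cost consequences analysis will be performed, whereby multiple outcomes are to be presented alongside costs". The outcomes listed beside it are correctly revised diagnoses, the total of revised diagnoses, and changes of management intent by gestational-age band. None of them counts inappropriate revisions.

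Section 8, Study Safety, does foresee wrong revisions. It describes, with a qualifying perhaps, the leading clinical risk as the case where "the prospective management of a particular pregnancy is modified as a result of information made available by in utero MR imaging" and that information turns out to be inaccurate. Its example is MR worsening the prognosis. False reassurance is discussed separately and classed as an AE rather than an SAE. Both are sent to the DMEC; neither is carried into the economic analysis.

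**The concern.** The effect of adding MR to ultrasound is the number of decisions consistent with the outcome with MR, minus the number with ultrasound alone. The protocol's unit captures only one half of that difference. A decision turned from right to wrong adds nothing to the effect and takes nothing away, so it is treated like a decision left unchanged.

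This would hold even if the rule for calling a revision appropriate were beyond dispute. It matters because the ratio bears on the cost-effectiveness objective and hypothesis in section 2. An MR service that corrected and spoiled equal numbers of decisions would still be reported with a positive effect and a finite cost per unit of effect.

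**Working it through.** **Plan's own figure.** The protocol gives no value for the ratio, so there is none to reproduce. The base for illustration can be checked. Section 9 gives 750 recruited, 4% failed MR examinations, 10% lost to follow-up and 20% without a reference diagnosis: 750 × 0.96 × (1 − 0.10 − 0.20) = 504, the stated number of completed cases.

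**Inputs.**
- N = 504 cases with a reference outcome (section 9).
- About 5% of cases changed (section 9). That figure covers prognosis and management intent together and is conjectural, so it serves only as an illustration.
- Share of revisions that are right: not given; assumed 40% to 90%.
- Incremental cost per case: not given; written C and assumed constant.

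**Gross and net effect.** Let k be the decisions right both before and after MR, a those changed from wrong to right, and b those changed from right to wrong. On a two-point scale with a known outcome, every change is one or the other.

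- Right with ultrasound alone: k + b. Right with MR: k + a. Difference: (k + a) − (k + b) = a − b.
- As written: appropriate revisions with MR = a; with ultrasound alone = 0; difference = a, which is never below 0.
- Ratio as written = N·C/a. Ratio on the net effect = N·C/(a − b).
- The net ratio exceeds the written one by a/(a − b). C and N cancel.

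**Numbers.** Changed decisions = 0.05 × 504 = 25.2.

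| Share right (assumed) | a | b | a − b | Ratio as written | Ratio on net effect | Factor |
|---|---|---|---|---|---|---|
| 90% | 22.7 | 2.5 | 20.2 | 22.2 C | 25.0 C | 1.13 |
| 75% | 18.9 | 6.3 | 12.6 | 26.7 C | 40.0 C | 1.5 |
| 60% | 15.1 | 10.1 | 5.0 | 33.3 C | 100.0 C | 3 |
| 50% | 12.6 | 12.6 | 0 | 40.0 C | undefined | none |
| 40% | 10.1 | 15.1 | −5.0 | 50.0 C | net harm | none |

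The factor depends only on the share right. With the 13.5% and 46% management-change rates that the Introduction cites from two earlier studies, an even split gives a = 34 or 116 and a − b = 0.

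**Can the wrong revisions be recovered from the planned outputs?** Only if both totals use the same cases. Section 8, Lost to Follow-Up, keeps cases without a reference diagnosis in the analysis of management change, while appropriateness needs a reference. Suppose the management-change total uses all 750 × 0.96 = 720 scanned cases. Then 5% gives 36 changes. At an assumed 80% right among the 504, 0.8 × 25.2 = 20.2 are appropriate. Subtraction gives 36 − 20.2 = 15.8 apparently wrong, against a true 5.0. The other 10.8 are merely unverified.

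**The case against.** The best defence is that the outcome is labelled incremental against ultrasound alone, which normally means a difference between strategies, and that an analysis plan could compute it so. The protocol never says that wrong revisions score zero. But it fixes the unit as decisions appropriately revised, in two sections, with a matching classification rule. Ultrasound alone has no revised decisions, so the difference in that unit is the gross count.

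Second, this is a cost-consequences analysis with other outcomes beside the ratio. On a binary scale, wrong revisions equal all changes minus appropriate ones. That stands in part: the harm is not hidden if the totals share a base. The protocol plans no such subtraction, though, and it would leave the ratio and the curve unchanged.

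Third, one-for-one netting treats the two kinds of wrong decision as equal, and section 4 is wary of single valued metrics in this setting. This is fair, and it is why both counts should be reported as well as the net.

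A reader might also infer more than the protocol supports:
- That MR's harms escape the whole study. They do not. The primary McNemar comparison of accuracy sets diagnoses MR spoils against those it corrects, and harmful cases go to the DMEC. The McNemar test on management does not help, however, because it compares whether termination was discussed, not whether the decision was right.
- That the protocol ranks wrong revisions in both directions as the foremost risk. Its statement is hedged and illustrated in one direction, with false reassurance handled separately.
- That the acceptability curve must climb to certainty. The protocol does not say how sampling uncertainty will be generated, so its limit cannot be stated.

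**Conclusion.** The point holds for one ratio in an ancillary sub-study. Followed as written, the effect measure cannot be negative. The ICER and its acceptability curve are therefore too favourable whenever MR causes any wrong revision, and they cannot show net harm.

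The size is unknown, because the protocol gives no share of right revisions. The understatement is modest if nine in ten are right, threefold at six in ten, and negligible if nearly all are right. These figures rest on assumed shares and on the same incremental cost in both versions of the ratio; they demonstrate no actual bias in the study. Primary diagnostic accuracy is untouched. It should be fixed, but it does not threaten the main conclusions.

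**What to change.** In sections 4 and 8, define the effect for the ratio, the plane and the acceptability curve as appropriate minus inappropriate revisions among cases with a reference outcome. State that this equals the paired difference in decisions consistent with the outcome, with and without MR. Report the two counts separately beside it, so that readers who weigh the two kinds of error differently can do so. Report management changes without a reference outcome as a third group.

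The change is one of wording and calculation; the same forms and reference diagnoses serve. The cost is a less favourable and less precise ICER, which may be undefined or unstable if the net effect is near zero.
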